Formulation	Sprays	Formulations	Sprays
CTY-5339-A	1	CTY-5339-CB	1
CTY-5339-A	2	CTY-5339-CB	1
CTY-5339-CB	1	CTY-5339-A	1
CTY-5339-CB	1	CTY-5339-A	2

To maintain double-blind conditions, the CTY-5339-CB subjects in the two spray sequences will also receive one spray with the vehicle control (CTY-5339-P). A third party not involved with evaluating subjects will administer the drug. The CTY-5339-P Vehicle will be sprayed outside the circumscribed area to avoid dilution of active drug. Efficacy evaluations will be done at 1-5 minute intervals beginning immediately after drug administration and will include:

Pin Prick (PPT) & QST Heat Sensation Tests:

For PPT, evaluations will be done at 1 minute intervals for the first 5 minutes to capture onset of anesthesia. Starting at 5 minutes after drug administration, both PPT and QST will be done at 5 minute intervals up to the one hour time point. If there is no indication of anesthesia by 10 minutes, the subject will be considered a treatment failure and the assessment of PPT and/or QST, as appropriate, will be discontinued. In addition, once onset of anesthesia has occurred, if there is no longer any anesthesia at two consecutive evaluation time points from 10 minutes onward, the assessment of PPT and/or QST, as appropriate, will be discontinued.

STUDY

Pin Prick Test (PPT): The PPT will be assessed, using a 90-mm, 26-

DESIGN: (cont) 1 gauge pencil-point spinal needle (Polymedic; Temena S.A., Bondy, France or equivalent). At screening, 3 pin pricks will be performed on each cheek. Pin pricks will be assessed using a 0 (no pain) to 10 (severe pain) Numerical Rating Scale (NRS). In order to be eligible for the study, for each cheek, subjects must have a minimum score of "3" for the last 2 pin pricks, and one of those scores has to be "4" or higher.

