mean Heat sensation threshold of 48.5°C or less, based on the last 2 of the 3 readings. Post-Baseline, the presence of analgesia/anesthesia will be defined when the heat sensation threshold at the treated site is higher than the Baseline (“Responder”).

All tests on the treated cheek will be done near the center of the circumscribed area, but in a slightly different place at each consecutive evaluation time point. All tests on the non-treated cheek will be performed at approximately the same part of the cheek as those on treated cheek.

Randomization: A randomization code will determine the sequence of treatments and to which circumscribed area the treatment is administered (left or right cheek). Sensory testing will be done in the following order: pin prick followed, where applicable, immediately by heat sensation tolerance.

Subjects retain the right to withdraw from the study at any time.

EFFICACY MEASUREMENTS

The primary comparison of interest is one spray of CTY-5339-A compared to one spray of CTY-5339-CB. Co-primary efficacy variables are duration of effect as determined by PPT and duration of effect as measured by QST Heat. Duration of effect is defined as the time (in minutes) from onset to treatment failure (for PPT, treatment failure occurs when an assessment of “Same/More” pain, and for QST, a treatment failure occurs when the average heat temperature is the same or less than the average heat temperature at Baseline up to the 60-minute time point (at two consecutive time points).

The secondary efficacy variables include:

- Duration of anesthesia (PPT and QST Heat) for the two sprays of CTY-5339-A compared to one spray of CTY-5339-CB plus CTY-5339-P
- Duration of anesthesia (PPT and QST Heat) for the two sprays of CTY-5339-A compared to one spray of CTY-5339-A
- Onset of anesthesia for PPT and QST Heat
- Percentage of responders for PPT and QST Heat for both onset and duration
- Percentage of responders for PPT and QST Heat at each time point

OTHER MEASUREMENTS

At Baseline and at the end of the 60-minute test session an ECG, vital signs, and a 7 mL blood draw will be taken. The blood will be analyzed for the occurrence of subclinical methemoglobinemia by the HUP – Pepper Lab via co-oximetry analysis. At screening and throughout each test session, subjects will also be monitored with pulse oximetry. Methemoglobinemia is being defined as >5% of a subject’s

hemoglobin in the methemoglobin state, or a pulse oximetry reading of less than 91%.

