8.4 Hypothesis

The following hypotheses will be tested to analyze the primary outcomes of the study:

- The null hypothesis that the duration of anesthesia (PPT and QST Heat) for the one spray CTY-5339-A group is the same as the corresponding duration for the CTY-5339-CB one spray group will be tested against the alternative hypothesis that the means are not equal.

The following hypotheses will be tested to analyze the secondary outcomes of the study:

- The null hypothesis that the duration of anesthesia (PPT and QST Heat) for the two spray CTY-5339-A group is the same as the corresponding duration for the CTY-5339-CB one spray plus CTY-5339-P one spray group will be tested against the alternative hypothesis that the means are not equal.
- The null hypothesis that the onset of anesthesia (PPT and QST Heat) for the CTY-5339-A groups is equal to the corresponding onset for CTY-5339-CB group will be tested against the alternative hypothesis that the means are not equal.
- The null hypothesis that the onset time until the first responder event (PPT and QST Heat) for the CTY-5339-A groups is equal to the corresponding onset time until a first responder event for CTY-5339-CB group will be tested against the alternative hypothesis that the event times are not equal.
- The null hypothesis that the duration time until the first non-responder event (QST and PPT) for the CTY-5339-A groups is equal to the corresponding duration time until the first non-responder event for CTY-5339-CB group will be tested against the alternative hypothesis that the event times are not equal.

The predicted outcome is that CTY-5339-A when locally applied to cheek mucosal tissue in the mouth will have an onset comparable to the fastest constituent, benzocaine, and a prolonged effect comparable to the longest acting constituent, tetracaine, of the combination product. The study also is designed to demonstrate that both the CTY-5339-A one and two-spray dosages are safe. (The assumption is made that benzocaine has a faster onset of action than tetracaine HCl.)

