13.5 Statistical Methods for Efficacy Evaluations

The primary efficacy analyses will be based on Modified Intent-to-Treat Population. The key comparisons will include:

1. CTY-5339-A, one spray versus CTY-5339-CB, one spray

The co-primary efficacy variables are duration of effect as measured by PPT and QST Heat. Duration of effect is defined as the time (in minutes) from onset to treatment failure (*i.e.*, for PPT, an assessment of “Same/More” pain, and for QST, the average heat temperature is greater than the average heat temperature at Baseline (non-treated cheek), up to the 60-minute time point (at two consecutive time points). For those discontinuing from the study for any other reason, the time to treatment failure will be censored at the last assessment time.

The secondary efficacy variables include:

- Duration of effect (PPT and QST) for CTY-5339A two sprays versus CTY-5339-CB, one spray plus CTY-5339-P one spray

- Duration of effect (PPT and QST) for CTY-5339A two sprays versus CTY-5339-A one spray
- Onset of anesthesia in minutes for PPT and QST Heat
- Percentage of responders at each time point for PPT and QST Heat for both onset and duration

Continuous variables will be analyzed via an ANOVA model with treatment effects at each of assessed time points. Pairwise comparisons for variables related to percentages will be analyzed via chi square tests. The 95% confidence intervals of the treatment differences will be presented using normal approximation with continuity correction, if appropriate. Pairwise comparisons for time-to-event related variables will be analyzed via a log rank model with treatment effects. Median time to event will be estimated and the 95% confidence intervals for the median will be presented, if appropriate.

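### The last secondary hypothesis in Section 8.4 ends duration at a single non-responder reading, the synopsis and Section 13.5 require two consecutive failures, and the log-rank test is tied to neither

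*Combined protocol and SAP*

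**What the plan says.** Section 8.4 introduces a list with "The following hypotheses will be tested to analyze the secondary outcomes of the study". The last item compares "the duration time until the first non-responder event (QST and PPT) for the CTY-5339-A groups" with the same quantity for CTY-5339-CB, and its alternative is that the event times differ. No confirming reading is mentioned. Appendix 2 and the synopsis define a responder separately at each time point.

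The duration definitions differ from this. The synopsis (Efficacy Measurements) runs duration from onset to treatment failure and, for QST, counts failure when the temperature is no higher than the "average heat temperature at Baseline up to the 60-minute time point (at two consecutive time points". Section 13.5 carries the same qualifier: "up to the 60-minute time point (at two consecutive time points". The synopsis rule for ending assessments also needs two readings: "if there is no longer any anesthesia at two consecutive evaluation time points from 10 minutes onward".

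On the test, Section 13.5 says only: "Pairwise comparisons for time-to-event related variables will be analyzed via a log rank model with treatment effects". It also censors time to treatment failure for subjects who discontinue for other reasons. The primary hypothesis in Section 8.4 is about means: it "will be tested against the alternative hypothesis that the means are not equal".

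**The concern.** Two quantities called duration have different end events. The item in Section 8.4 covers both CTY-5339-A groups, so it includes the one-spray comparison that is also the primary one. It is the only duration hypothesis in that section framed as event times, which makes it a natural candidate for the log-rank test. Yet the confirmed-failure duration in Section 13.5 is censored time-to-event data and is an equally natural candidate. Two statisticians could follow the plan and report different duration curves, and the choice could be made after the data are seen.

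The choice matters because a single-reading rule has no protection against one chance failure. A longer-acting product has more readings at risk before it wears off, so chance failures shorten its measured duration most and shrink the difference between products.

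**Working it through.** **Plan's own figures.** The plan gives no reading error rate, expected duration, SD or power, so there is no figure to reproduce on this point. The exposure count is consistent: 38 + 38 + 76 = 152 = 76 × 2.

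**Hand check on a 5-minute grid.** Assume onset at 5 minutes, fixed wear-off at 40 (A) and 25 (CB) minutes, and independent chance non-response q at each numb reading. With m grid steps from onset to wear-off, the expected duration to the first failure is 5 × [1 − (1 − q)^m] / q. Here m = 7 for A and 4 for CB, so the difference is 5 × [(1 − q)^4 − (1 − q)^7] / q. At q = 0.10 this is 5 × (0.6561 − 0.4783) / 0.10 = 8.9 minutes, against a true 15.

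| q | First event (min) | Loss | Two consecutive (min) |
|---|---|---|---|
| 0.02 | 13.6 | 10% | 15.0 |
| 0.05 | 11.6 | 23% | 14.8 |
| 0.10 | 8.9 | 41% | 14.3 |
| 0.15 | 6.7 | 55% | 13.6 |
| 0.20 | 5.0 | 67% | 12.6 |

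**PPT simulation** (200,000 sessions per setting). From the documents: readings at 1, 2, 3, 4 and 5 minutes, then every 5 minutes to 60. Assumed: onset at 2 minutes, wear-off mean 40 (A) and 30 (CB) with SD 10, 5% false response after wear-off, independent errors, and failure dated at the first reading of a confirmed pair. The pair is counted from 10 minutes; the first-event rule counts from the first reading after onset. The true difference is 10 minutes.

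| Chance non-response | First event: A−CB (min) | Standardised | Two consecutive: A−CB (min) | Standardised |
|---|---|---|---|---|
| 2% | 8.2 | 0.63 | 9.7 | 0.96 |
| 5% | 6.1 | 0.41 | 9.6 | 0.93 |
| 10% | 3.9 | 0.25 | 9.2 | 0.86 |
| 15% | 2.5 | 0.16 | 8.7 | 0.77 |

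Repeat runs agree to about 0.1 minute. Against the true 10 minutes, the first-event rule loses 18, 39, 61 and 75%, and the two-consecutive rule 3, 4, 8 and 13%.

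**What error rate is conceivable?** For PPT the worse of two pricks counts (Appendix 2). An assumed 5% error per prick gives 1 − 0.95² = 9.8% per reading, and 8% gives 1 − 0.92² = 15.4%. These show that 10 to 15% is possible, not that it applies.

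**QST.** Any rise above Baseline counts as a response, so chance responses after wear-off could be frequent. Assume 50%, a 5-minute grid, onset at 5 minutes, and wear-off 35 v 25 minutes with SD 10 (true difference 10).

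| Chance non-response | First event: A−CB (min) | Two consecutive: A−CB (min) |
|---|---|---|
| 0% | 9.4 | 7.0 |
| 2% | 8.4 | 6.9 |
| 5% | 6.9 | 6.8 |
| 10% | 5.0 | 6.4 |

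Below about 5% the first-event rule keeps more of the difference. Above that it keeps less.

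**The case against.** The affected item is one secondary hypothesis in a proof-of-concept study. The primary hypothesis compares means and does not use first-event wording. Both points stand and limit the weight of the finding.

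The phrase might mean the first reading of a confirmed pair, or the item might be a deliberate extra, since onset also gets both a means hypothesis and a first-event hypothesis. Either is possible. The secondary outcome list in Section 8.3.2 names no such endpoint, but that does not prove a slip. It remains an ambiguity that the text should settle.

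The PPT comparison is uneven, because the 10-minute start belongs to the rule for ending assessments and not to the duration definitions. Starting both rules at 10 minutes, the first-event difference is 7.3, 5.3 and 3.9 minutes at 5, 10 and 15% error, against 9.6, 9.2 and 8.7. A loss over half of the true 10 minutes then appears only at 15%. Section 8.4 states no 10-minute start, so the larger loss follows from its literal wording, but part of it comes from the early readings.

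A reader might infer that the two-consecutive rule is always the less noisy. The QST table does not support that. On log-rank power in that setting (38 per arm, 600 simulated trials), the first-event rule is still slightly ahead at 10% error, 0.42 against 0.37.

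**Conclusion.** The inconsistency is real and nothing in the documents reconciles it. Followed literally, Section 8.4 tests a different secondary endpoint from the duration defined in the synopsis and Section 13.5, and the input to the log-rank test is left open.

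The size is conditional. For PPT under the stated assumptions, the single-reading rule loses about 18% of a true 10-minute difference at 2% error per reading and 39% at 5%. It passes half at roughly 10% or more. The error rates, wear-off times and SD are all assumed, reading errors are taken as independent, and the pairing of sessions within subjects is ignored.

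A reader might infer that the log-rank on duration is settled on the single-reading version, or that the primary analysis is compromised. The documents support neither: Section 13.5 links the test to no definition, and the primary hypothesis does not use this event. Nor do they support a flat claim that over half of the effect is lost. The case for alignment is that one name should mean one event, fixed before the data are seen.

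**What to change.** 1. In the last secondary hypothesis of Section 8.4, replace the first non-responder event with treatment failure at two consecutive time points, as defined in the synopsis efficacy measurements (PPT: a Same/More rating; QST: average temperature the same as or less than the treated-cheek Baseline).
2. Do not point to Section 13.5 for this definition as it stands. It words QST failure as a temperature above Baseline, which is the responder direction, and refers to the non-treated cheek, although session QST is measured on the treated cheek only. Correct both to match the synopsis.
3. State whether failure is dated at the first or the second of the two readings. On the 5-minute grid the choice moves each confirmed failure by 5 minutes.
4. Name this confirmed-failure duration as the duration endpoint for the log-rank test.
5. Label any analysis of time to first non-responder as a sensitivity analysis.

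The cost is one sentence in Section 8.4 and short edits to Section 13.5. No new data are needed.

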9. SUMMARY OF STUDY DESIGN

This is a single-dose, double-blind and single-center study with an active control treatment. All subjects will remain at the study center for each of the two 60 minute test sessions. The volunteer subjects will be tested at two different test sessions separated by 4-14 days and serve as their own control.

The study will include 76 subjects with 60-minute evaluations at each test session.

At each session, a circular area of approximately 1 inch in diameter will be isolated on one side of the cheek. Each session will use a different side of the cheek. The possible sequences of treatments at the two sessions are:

Session 1		Session 2	
Formulation	Sprays	Formulations	Sprays
CTY-5339-A	1	CTY-5339-CB	1
CTY-5339-A	2	CTY-5339-CB	1
CTY-5339-CB	1	CTY-5339-A	1
CTY-5339-CB	1	CTY-5339-A	2

(To maintain double-blind conditions, the CTY-5339-CB subjects in two spray sequences will also receive one spray with the vehicle control (CTY-5339-P) just outside the circumscribed area. A third party not involved with evaluating subjects will administer the drug.)

For PPT, evaluations will be done at 1-minute intervals following drug administration for the first 5 minutes to capture onset of anesthesia. Starting at 5 minutes after drug administration, both PPT and QST will be done at 5-minute intervals up to the one hour time point. Once onset has occurred, if there is no analgesia at two consecutive evaluation time points (from 10 minutes onward), the session will be discontinued. In addition, if onset of analgesia has not occurred by 10 minutes post dose, the subject will be considered a treatment failure and no further assessments will be made.

PPT: The PPT will be assessed, using a 90-mm, 26-gauge pencil-point spinal needle (Polymedic or equivalent; Temena S.A., Bondy, France or its equivalent). At each post dosing time point, PPT will be assessed in 3 repetitions on the non-treated site using a 0-10 Numerical Rating Scale (NRS) with "0" as no pain and "10" as severe pain. PPT will then be assessed in 3 repetitions on the treated site. These assessments will be compared to the contra-lateral, non-treated site as "No pain", "Less Pain" or "Similar/More Pain". "No Pain" or "Less Pain" at an application site will be recorded as presence of analgesia/anesthesia ("Responder").

QST: The heat stimuli are delivered in 3 repetitions, with inter-stimulus intervals of 30s. The basal thermode temperature is set at a comfortable 35°C. The rate at which the thermode heats up is set at 0.5°C/s, while the rate at which it cools down is set at 8°C/s. The maximum thermode temperature is set at 51°C. The first stimulus is disregarded and the remaining two stimuli are averaged for data analysis. In situations where a maximal analgesia/anesthesia effect is demonstrated in the initial two repetitions, the QST test will not be repeated for the third repetition and the data will be recorded as maximal effect (51°C) based on the first two repetitions.

Heat sensation threshold will be defined as the temperature at which the subjects first start to feel tingling, warmth, heat, or pain. All tests will be done near the center of the circumscribed area, but in a different place at each evaluation time point. For QST, the first time point after Baseline will begin at 5 minutes after drug administration. Subjects will have a hand held mouse that turns off the heat probe when they first start to feel tingling, warmth, heat, or pain. At the maximum heat level of 51° C, the heat probe turns off automatically. With a brief exposure at 51° C, there is no damage to the mucosal tissue.²⁵

Randomization: A randomization code will determine in which circumscribed area each treatment is administered (left or right cheek). Immediately prior to beginning each 60 minute test session, both the contra-lateral cheek and the cheek to be dosed will be evaluated with the PPT. For QST, the screening assessments will be performed on both cheeks, while during each treatment Session, at Baseline and all post-dosing time points, assessments will be performed on the treated cheek only.

Subjects retain the right to withdraw from the study at any time.

The PPT and QST tests will be done near the center of each evaluation area but in a different place at each evaluation time point. For PPT, the non-treated control cheek will always be tested before the treated area. The testing will be done in the following order where applicable: PPT and then QST.

A safety phone follow-up call will occur 3 days (± 1 day) after the Session 1 and 15 days (± 2 days) following Session 2.

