11.2.3 Post-Baseline Assessments

The time points of the post-baseline efficacy assessment are detailed in section 9 of this protocol. The PPT will be performed on both the control and treatment sites at each evaluation time point. The QST will be performed only at the treatment site for the post baseline evaluation time points.

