13.2 Analysis Populations

There will be three analysis populations:

Safety population: will include all randomized subjects who received the study medication. This population will be used for all safety summaries.

Intent-to-Treat (ITT) population: will include all randomized subjects who dosed with study medication and provided a Baseline assessment. All secondary efficacy analyses and summaries will be performed using this population.

Modified Intent-to-Treat (mITT) population: will include all randomized subjects who, as documented prior to the breaking of the study blind: (1) met all the inclusion and exclusion criteria and; (2) either completed the two 60 minute test sessions or returned to baseline values in all the evaluation tests. The primary efficacy analyses will be performed using this population.

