13.6 Multiple End Points and Multiple Comparisons

Duration of Effect, as assessed by PPT and QST Heat are co-primary efficacy parameters. In order to control the overall significance level for the two primary endpoints, the total alpha level of 0.1 is Bonferroni adjusted to $0.10/2 = 0.05$ (since this is a proof of concept study, the total alpha level of 0.1 instead of 0.05 has been selected). The study will be considered successful if either of the two primary endpoints is statistically significant.

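### The synopsis stops PPT and QST test by test, but Section 9 stops the session without naming the triggering test, so one co-primary duration could cut off the other

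*Combined protocol and SAP*

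**What the plan says.** The synopsis (Study Design, Pin Prick and QST Heat tests) schedules PPT every minute to 5 minutes, then PPT and QST every 5 minutes to 60 minutes. It has two triggers for stopping: no onset by 10 minutes, and no effect at two consecutive points (from 10 minutes on) once onset has occurred. In both cases what stops is the test concerned: "the assessment of PPT and/or QST, as appropriate, will be discontinued".

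Section 9 repeats both triggers with different consequences. After onset, "if there is no analgesia at two consecutive evaluation time points (from 10 minutes onward), the session will be discontinued". Without onset by 10 minutes, "the subject will be considered a treatment failure and no further assessments will be made". Neither sentence names a test.

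Other sections that bear on this:

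- 11.2.3: "The time points of the post-baseline efficacy assessment are detailed in section 9 of this protocol".
- 13.2, mITT set (used for the primary analysis): besides meeting the entry criteria, a subject must have "either completed the two 60 minute test sessions or returned to baseline values in all the evaluation tests".
- 13.5, following the definition of failure at two consecutive points: "For those discontinuing from the study for any other reason, the time to treatment failure will be censored at the last assessment time".
- 13.6, on PPT duration and QST duration as co-primaries: "The study will be considered successful if either of the two primary endpoints is statistically significant".

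**The concern.** PPT duration and QST duration are separate endpoints, each with its own failure criterion, and either one alone can make the study a success. Each therefore has to be observed until its own failure or 60 minutes. The synopsis provides for that. Section 9 can be read as ending all testing once one test has failed. On that reading the longer-lasting endpoint would be censored at a time set by the other endpoint, in the same subject and at the same anesthetized site. Such censoring is likely to be informative, whereas the log-rank comparison in 13.5 needs it not to be. Observations that are not taken cannot be recovered later.

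**Working it through.** No figure in the plan depends on this rule, so there is none to reproduce. The check compares the texts and then works through the protocol's own assessment times.

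**Step 1. The texts side by side.**

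| Situation | Synopsis | Section 9, either test triggers | Section 9, both tests needed |
|---|---|---|---|
| PPT has failed twice, QST still above baseline | PPT stops, QST goes on | All testing stops | Session goes on; no separate stop for PPT |
| PPT has onset, QST has none by 10 min | QST stops, PPT goes on | All testing stops | Session goes on; no separate stop for QST |
| Both tests have failed twice | Both stop | Session stops | Session stops |

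The texts agree only in the last row. Section 9 does not say which of its two columns applies.

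**Step 2. Loss of effect after onset.** Suppose QST onset is at 5 min, PPT fails at 20 and 25 min, and QST would fail at 45 and 50 min.

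- Synopsis: QST is taken at 5, 10, ..., 50 min, which is (50 − 5)/5 + 1 = 10 points. Duration = 45 − 5 = 40 min.
- Section 9, either test: the session ends after the 25-min assessment. QST is taken at 5 to 25 min, which is (25 − 5)/5 + 1 = 5 points. QST is still above baseline at 25 min, so its duration is known only to exceed 25 − 5 = 20 min. The points at 30, 35, 40, 45 and 50 min are lost (10 − 5 = 5).
- Section 9, both tests: QST is followed to 50 min and nothing is lost.

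**Step 3. No onset by 10 minutes.** By then PPT has been tested at 1, 2, 3, 4, 5 and 10 min (six times) and QST at 5 and 10 min (twice). Suppose PPT has onset at 2 min and still shows effect at 10 min, while QST shows none. Under the synopsis PPT continues, with up to (60 − 15)/5 + 1 = 10 points from 15 to 60 min. On the either-test reading all of these are lost, and PPT duration is known only to exceed 10 − 2 = 8 min.

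**Step 4. What the analysis sections do with the cut-off test in Step 2.**

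- 13.5 censors subjects who leave the study. A session ended because the other test failed is not leaving the study, so no rule is written for it. Failure needs two consecutive points, so a test stopped after one failing point has not met the definition, and 13.5 does not say how to handle it.
- 13.2: the session did not run to 60 minutes, and QST had not returned to baseline. The subject meets neither limb of the mITT condition. Because the set is defined by subject, the other session would be lost as well.

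**Step 5. Illustration only.** The documents give no means, variances or correlations, so every input here is assumed: lognormal durations, onset at 5 min, PPT–QST correlation 0.5, CV 50%, either-test reading.

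- With mean durations of 25 min on both tests, one test is stopped before its own two-point failure in about 79% of sessions. This includes tests already failing once; one test is still above baseline in about 46%. Over means of 20–30 min, CV 30–70% and correlation 0.3–0.8, the ranges are 51–93% and 7–64%.
- With means of 30 versus 20 min, 38 sessions per arm and an unpaired log-rank test at 0.05, QST power is about 93% under the synopsis rule. It is about 66% if a single failing last point is censored and about 89% if that point counts as the event. The chance that at least one co-primary succeeds goes from about 98% to about 91%, or stays at about 98%.

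These power figures keep sessions that the literal mITT definition would exclude, so they do not describe the primary analysis exactly.

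**The case against.** The strongest reply is that the harmful reading is the least supported one. The synopsis states the test-by-test rule explicitly for both triggers. Section 9 is headed as a summary, itself schedules both tests to one hour, and can be read as ending the session once neither test shows any effect. The mITT wording in 13.2 presupposes follow-up until all tests are back at baseline. No sentence says that failure on one test stops the other. All of this stands, and it makes the harm conditional. It does not remove the conflict: Section 9 names no test, and even the both-tests reading lacks the separate stop that the synopsis requires.

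Three stronger inferences are tempting, and the documents support none of them.

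- A reader might infer from 11.2.3 that Section 9 overrides the synopsis. The reference is to time points, not to stopping rules.
- A reader might infer that different evaluators would generate different durations. Section 10.4 has one team do all evaluations, so the realistic risk is a single choice of reading for the whole study.
- A reader might take the fall in QST power from 93% to 66% as the expected loss. It rests wholly on assumed inputs, the less supported reading and the strictest handling of a single failing point. It also assumes the log-rank test of 13.5, whereas the synopsis names ANOVA and t-tests. Success needs only one co-primary, and on the same inputs that chance changes much less.

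It is also fair to say that the event definition is not missing. The synopsis and 13.5 both require two consecutive failing points. The secondary hypothesis in 8.4 on the first non-responder event does not change that for the primary endpoints. The open question is only how to treat a test whose testing ends before its second failing point.

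**Conclusion.** The plan is wrong as written, as an internal contradiction. The synopsis and Section 9 give different stopping instructions for efficacy testing whenever PPT and QST fail at different times, and nothing in the document settles which applies. That finding rests on the text alone and is firm.

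The consequence is conditional. If Section 9 is applied when one test fails, the other co-primary duration is cut off (40 minutes becoming more than 20 in the example), probably with informative censoring. Section 13.5 then has no rule for the stop, and the subject may drop out of the mITT set. If both tests must fail, or if the synopsis is followed, no duration is lost. The plan does not establish that durations will be truncated, and its figures do not allow the loss of power to be estimated.

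**What to change.** Reconcile the synopsis and Section 9 into one efficacy-testing statement, used in both places, that names the test it applies to. It should cover both the 10-minute trigger and the two-point trigger, so that failure on one co-primary does not end observation of the other, as the synopsis already provides.

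Then match two sections to it:

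- 13.2: judge return to baseline test by test under that statement.
- 13.5: say how a test's duration is handled when its testing ends without its own two-point failure, including when the last point taken is a single failing one.

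The cost is an aligned paragraph in Section 9 and one sentence each in 13.2 and 13.5. No testing is added beyond what the synopsis already requires.
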